## 10.2. Selection of Sample Size

Approximately 63 eligible subjects (Up 30 in Dose Escalation and up to 33 in Safety Expansion) in Phase 1 will be included in this study.

### 10.2.1. Sample Size for Dose Escalation

We will employ the Bayesian optimal interval (BOIN) design ([Liu 2015](#); [Yuan et al. 2016](#)) to guide dose escalation and establish the MTD or the optimal biologically active recommended Phase 2 dose (RP2D) for NC525.

The target toxicity rate for the MTD is  $\phi = 0.25$  and the maximum sample size per cohort is 12. We will enroll and treat subjects in cohorts of size 3. DLTs are defined in [Section 5.9](#). The steps to implement the BOIN design are described as follows:

1. To minimize the chance of exposing subjects to potentially subtherapeutic doses, perform the accelerated titration at dose level 1 (DL1) as follows: treat the first subject at DL1, if a DLT or two or more grade 2 toxicities are observed, treat 2 additional subjects at DL1; otherwise escalate to DL2 and hereafter treat subjects in cohort size of 3.
2. To assign a dose to the next cohort of subjects, conduct dose escalation/de-escalation according to the rule displayed in [Table 1](#) (or equivalently [Figure 2](#)). When using Table 1/[Figure 3](#), please note the following:
  - If the criteria is met to escalate the dose, dose escalation will be evaluated against the Dose Increment Modification Rule ([Table 2](#)).
  - “Eliminate” means eliminate the current and higher doses from the trial to prevent treating any future subjects at these doses because they are overly toxic.
  - When we eliminate a dose, automatically de-escalate the dose to the next lower level. When the lowest dose is eliminated, stop the trial for safety. In this case, no dose should be selected as the MTD.
  - If none of the actions (i.e., escalation, de-escalation or elimination) is triggered, treat the new subjects at the current dose.
  - If the current dose is the lowest dose and the rule indicates dose de-escalation, treat the new subjects at the lowest dose unless the number of DLTs reaches the elimination boundary, at which point terminate the trial for safety.
  - If the current dose is the highest dose and the rule indicates dose escalation, treat the new subjects at the highest dose.
3. Repeat step 2 until the maximum sample size of 30 is reached or stop the trial if the number of evaluable subjects treated at the current dose reaches 9 and the decision according to the rules described in Step 2 is to stay at the current dose.

The sample size of dose escalation is not based on conventional power calculation, but chosen to be consistent with typical phase I oncology trials and calibrated using simulation. Below provides the operating characteristics of the trial design based on 1000 simulations of the trial using shiny app "BOIN" (BOIN V2.7.6.0), showing that the design selects the true MTD, if any, with high probability and allocates more patients to the dose levels with the DLT rate closest to the target of 0.25.

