**Figure 2: Dose Finding Rules Per BOIN**

## 3.2. Study Phase and Cohorts

### 3.2.1. Phase 1 Design

[figure not shown]
A BOIN design will be utilized to determine the MTD of NC525, where a minimum of 3 evaluable subjects will be enrolled at each level from Cohort 2 onwards. In the case of the starting dose level (2mg/kg), a minimum of 1 evaluable subject may be enrolled (in the absence of severe toxicity) prior to determining escalation to the next dose level given the dose is an approximation of the minimally active dose (PD30).

All dose escalation decisions will be based on the occurrence of DLTs at a given dose during the first 56-day period (i.e., first 2 cycles), also referred to as the DLT observation period (Figure 3). Dose escalation decisions will be made jointly by the Clinical Study Team comprised of the

[figure not shown]
Sponsor Medical Monitor, CRO Medical Monitor and Investigators once the minimum number of evaluable subjects (n=3) have completed the DLT observation period.

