**Table 4: Dose Modifications for Adverse Events**

AE Toxicity grade (CTCAE V5.0)	Action with NC525
Grade 3 Immune-related AE (e.g. pneumonitis, colitis, elevated LFTs (in absence of active disease), etc.)	Interrupt Treatment, Restart treatment at one dose level lower when the specific immune-related AE resolves to no more than Grade 1 in severity. If immune-related AE does not resolve in 14 days, or if the Grade 3 immune-related AE recurs, the subject must permanently discontinue.
Grade 4 Immune-related AE (e.g. pneumonitis, colitis, elevated LFTs (in absence of active disease), etc.)	Permanently Discontinue

AE Toxicity grade (CTCAE V5.0)	Action with NC525
Grade 3 or Grade 4 Tumor Lysis Syndrome (TLS)	
Interrupt Treatment, Restart treatment at the same dose when the TLS is resolved to no more than Grade 1 in severity within 2 weeks or 14 days,
 
For Management of TLS, see Appendix 5

Any Grade Infusion Reaction	See Table 5 for management of infusion reaction.
(Grading based on reporting of individual symptoms)	
Interrupt Treatment, Administer corticosteroids per standard of care. Restart treatment at the same dose level with the DS is resolved within 2 weeks or 14 days.

New Onset Grade 4 Neutrophil Count Decrease lasting > 1 week b	
Interrupt Treatment, Restart treatment at the same dose when the ANC is <math>\geq 500/\mu\text{L}</math> within 2 weeks or 14 days.
 
If Grade 4 neutropenia recurs, interrupt again but restart at one dose level lower when the ANC is <math>\geq 500/\mu\text{L}</math> within 2 weeks or 14 days.

New Onset Grade 4 Platelet Count Decrease lasting > 1 week b	
Interrupt Treatment, Restart treatment at the same dose when the platelet count <math>\geq 25,000/\mu\text{L}</math> within 2 weeks or 14 days.
 
If Grade 4 thrombocytopenia recurs, interrupt again but restart at one dose level lower when the platelet count is <math>\geq 25,000/\mu\text{L}</math> within 2 weeks or 14 days.

Any other non-hematological Grade 3 (other than TLS) adverse reaction	
Interrupt Treatment, Restart treatment at the same dose if the adverse reaction resolved to no more than Grade 1 in severity within 2 weeks or 14 days.
 
If the adverse reaction recurs at Grade 4, the subject must permanently discontinue.
 
If the adverse reaction recurs a second time at Grade 3, interrupt again, and the subject must permanently discontinue.

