## **5.9. Dose Limiting Toxicities (DLTs)**

### **5.9.1. Dose-Limiting Toxicity and Determination of Maximum Tolerated Dose**

During Dose Escalation, the evaluation period for DLTs will begin on Cycle 1 Day 1 and will continue up to 56 days. All DLTs will be assessed by the investigator using National Cancer Institute Common Terminology Criteria for Adverse Events (NCI CTCAE) v5.0. A DLT will be defined as the occurrence of any toxicity in [Table 6](#), except for events clearly associated with the underlying disease or an extraneous cause (e.g., car accident).

Individual subject dose reductions may be made based on events observed at any time during treatment with NC525; however, for the purposes of dose cohort escalation/de-escalation, and expanding a dose cohort, the decisions will be made based on events that are observed from the first day of study treatment through and including the 56-day DLT period. Alternative dose levels may subsequently be determined based on relevant toxicities that become evident after the 56-day DLT period.

**Table 6: Definition of Dose-Limiting Toxicity National Cancer Institute Common Terminology Criteria for Adverse Events (NCI CTCAE) v5.0**

Nonhematologic toxicity

Any grade 3 nausea, vomiting or diarrhea that requires TPN, tube feeding, or hospitalization is a DLT without exception

Any other grade 3 adverse reaction (including laboratory abnormalities) lasting more than 72 hours, with the following exceptions:

Grade 3 fatigue lasting >3 days

Any grade 4 nonhematological adverse reactions.

Any Hy's law case defined as:

Combined elevations in serum ALT >3 times the upper limit of normal (ULN) and bilirubin >2 ULN in the absence of alkaline phosphatase (ALP) elevation (<2 ULN). Note: Abnormal liver function tests as indicated by the criteria above will be considered a DLT if no other reason can be found to explain the combination of increased liver markers such as viral hepatitis A, B, or C; preexisting or acute liver disease; or another drug capable of causing the observed injury

Hematologic toxicity

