**Table 12: NCI CTCAE v5.0 Grading Scale**

Grade	Clinical Characteristics
Grade 1	Mild; asymptomatic or mild symptoms; clinical or diagnostic observations only; intervention not indicated.
Grade 2	Moderate; minimal, local, or noninvasive intervention indicated; limiting age-appropriate activities of daily living.

Grade	Clinical Characteristics
Grade 3	Severe or medically significant but not immediately life-threatening; hospitalization or prolongation of hospitalization indicated; disabling; limiting self-care activities of daily living.
Grade 4	Life-threatening consequences: urgent intervention indicated.
Grade 5	Death

The occurrence of AEs should be sought by nondirective questioning of the subject during the screening process after signing the ICF and at each visit during the study. Adverse events may also be detected when they are volunteered by the subject during the screening process or between visits, or through physical examination, laboratory test, or other assessments. To the extent possible, each AE should be evaluated to determine:

- The severity grade (NCI CTCAE v5.0 Grade 1 to 5).
- Relationship to study drug: unrelated, unlikely related, possibly related, probably related, and definitely related. See [Appendix 1](#).
- The start and end dates, unless unresolved at final follow-up.
- The action taken with study drug.
- The event outcome (e.g., not recovered/not resolved, recovered/resolved, recovering/resolving, recovered/resolved with sequelae, fatal, unknown).
- The seriousness, as per SAE definition provided in [Section 9.1.2](#).

All AEs should be treated appropriately. If an AE is treated with a concomitant medication or nondrug therapy (e.g., procedure), this action should be recorded on the AE eCRF and the event should be correlated as the indication on the appropriate eCRFs as applicable.

Once an AE is detected, it should be followed until it has resolved or until it is judged to be permanent; assessment should be made at each visit (or more frequently if necessary) of any changes in severity, the suspected relationship to the study drug, the interventions required to treat the event, and the outcome.

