#### **9.2. Laboratory Test Abnormalities**

Laboratory abnormalities that constitute an AE in their own right (considered clinically meaningful, induce clinical signs or symptoms, require concomitant therapy, or require changes in study drug) should be recorded on the AE eCRF. Whenever possible, a diagnosis rather than a symptom should be provided (e.g., "anemia" instead of "low hemoglobin"). Laboratory abnormalities that meet the criteria for AEs should be followed until they have returned to normal or an adequate explanation of the abnormality is found. When an abnormal laboratory test result corresponds to a sign or symptom of a previously reported AE, it is not necessary to separately record the laboratory test result as an additional event.

Laboratory abnormalities that do not meet the definition of an AE should not be reported as AEs. A Grade 3 or 4 (severe) AE does not automatically indicate an SAE unless it meets the definition of serious, as defined in [Section 9.1.2](#).

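### Section 10.2.1 step 1 and Section 3.2.1 set different conditions for escalating after one subject at Dose Level 1, and a single non-DLT Grade 3 event falls between them (minor)

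*Combined protocol and SAP*

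**What the plan says.** Two parts of the plan govern how many subjects are treated at DL1 (2 mg/kg every two weeks) before moving to DL2 (2.5 mg/kg weekly).

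- **Section 10.2.1, step 1:** after the first subject, "if a DLT or two or more grade 2 toxicities are observed, treat 2 additional subjects at DL1; otherwise escalate to DL2".
- **Section 3.2.1 and the synopsis (Study Phase and Cohorts), same wording:** "a minimum of 1 evaluable subject may be enrolled (in the absence of severe toxicity) prior to determining escalation to the next dose level".

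Neither place defines severe toxicity. Other sections use the word in two ways:

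- Table 12 (Section 9.1.6) describes Grade 3 as "Severe or medically significant but not immediately life-threatening", and Section 9.2 states: "A Grade 3 or 4 (severe) AE does not automatically indicate an SAE".
- The note under Table 17 (Section 10.2.2) builds its severe toxicity rate from Table 6 events, but only for the expansion stopping rule.

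Table 6 (Section 5.9.1) does not make every Grade 3 event a DLT. The general non-hematologic criterion is "Any other grade 3 adverse reaction (including laboratory abnormalities) lasting more than 72 hours", with Grade 3 fatigue exempt. The whole definition applies "except for events clearly associated with the underlying disease or an extraneous cause". Table 4 (Section 5.8.2) then handles two kinds of Grade 3 event without a dose reduction. For tumor lysis syndrome it says "Restart treatment at the same dose when the TLS is resolved to no more than Grade 1 in severity". For other non-hematologic Grade 3 reactions it says "Restart treatment at the same dose if the adverse reaction resolved to no more than Grade 1 in severity".

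**The concern.** DL1 is the only level at which a single subject can open the next dose in this first-in-human study. If severe means Grade 3 or higher, the two sections give opposite answers for the same subject, and the team would have to decide on the day which one governs.

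Step 1 is also oddly ordered. Two Grade 2 toxicities bring in two more subjects, while one Grade 3 toxicity that is not a DLT brings in none. At stake is whether one or three subjects are treated at 2 mg/kg before subjects receive 2.5 mg/kg weekly.

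**Working it through.** No figure in the plan corresponds to this point, so the main check applies each rule to the same first subject.

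| First DL1 subject has | DLT under Table 6? | Step 1 | 3.2.1, severe = Grade 3+ | 3.2.1, severe = DLT |
|---|---|---|---|---|
| One non-hematologic Grade 3 reaction, 72 h or less, restarted at same dose | No | Escalate | One-subject step not permitted | Permitted |
| Grade 3 tumor lysis syndrome resolved within 72 h, restarted at same dose | No | Escalate | Not permitted | Permitted |
| Grade 3 fatigue only | No (exempt) | Escalate | Not permitted | Permitted |
| Two Grade 2 toxicities | No | Add 2 subjects | Permitted | Permitted |
| Grade 3 infusion reaction | Yes (Table 5 discontinues; withdrawal is a DLT) | Add 2 subjects | Not permitted | Not permitted |

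The first three rows are the gap. It does not cover all Grade 3 events. Grade 3 immune-related events restart one dose level lower and so become DLTs through the dose-reduction criterion. Hy's law cases, and nausea, vomiting or diarrhea needing TPN, tube feeding or hospitalization, are DLTs outright.

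**Grade 2 or Grade 2 and above.** Reading step 1 as Grade 2 or higher does not close the gap, because one event is not two. There is a partial exception. Section 9.1.6 records each change of severity as a separate adverse event, so if step 1 counts records, an event seen at both Grade 2 and Grade 3 could count twice. An event with no Grade 2 phase would not.

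**Does the dose increment rule act as a backstop?** The caps in Section 3.2.2, applied from 2 mg/kg, are:

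- 100%: 2 × 2.0 = 4.0 mg/kg
- 50%: 2 × 1.5 = 3.0 mg/kg
- 30%: 2 × 1.3 = 2.6 mg/kg

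All exceed the planned 2.5 mg/kg, so none binds. The caps also govern dose size, not the number of DL1 subjects.

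**Size of the planned step, for every subject.** Per dose: 2.5/2 − 1 = 25%. Per 28-day cycle: DL1 gives 2 × 2 = 4 mg/kg and DL2 gives 4 × 2.5 = 10 mg/kg; 10/4 − 1 = 150%. Margin to the human equivalent of the NOAEL (Section 1.2.1): 85/2.5 = 34-fold.

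**One subject versus three, in general.** Assume subject 1 has no DLT and later subjects have independent DLTs with probability p. Take p from the DL1 column of Table 14; this is an assumption, since that table simulates five levels and Section 3.2.2 plans six. Table 1 escalates at n = 3 only with 0 DLTs and at n = 6 only with at most 1.

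- Not escalating at n = 3: 1 − (1 − p)².
- Still not escalating at n = 6: 2p(1 − p)[1 − (1 − p)³] + p².

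| p | n = 3 | n = 6 |
|---|---|---|
| 0.02 | 4.0% | 0.3% |
| 0.04 | 7.8% | 1.0% |
| 0.12 | 22.6% | 8.2% |
| 0.25 | 43.8% | 27.9% |

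These figures would be the same for a first subject with no toxicity at all. They describe accelerated titration, not this gap.

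**The case against.** The strongest reply is that severe toxicity means DLT. The only other place where the plan uses the phrase is the note under Table 17, which ties it to Table 6. Table 12 is a fallback scale for events that CTCAE does not classify, and Section 9.2 is only separating severe from serious. On that reading the conflict over Grade 3 events disappears. The objection makes the term contestable but does not settle it. The Table 17 note concerns the expansion phase, the grading text points to Grade 3, and the DL1 condition itself is undefined.

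Second, the subject in the gap is already well characterized. Section 3.2.1 requires an evaluable subject: at least four doses and 56 days, or earlier discontinuation for an adverse event. At every two weeks, four doses is the full two-cycle DL1 course, and withdrawal or dose reduction for an adverse reaction is itself a DLT. So, apart from a stop for an event not attributed to the drug, this subject has resolved the event, finished the course and had no DLT. That stands, and it narrows the concern considerably.

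Third, a reader might infer that step 1 forces escalation, or that nothing written would hold it. The documents support neither. The Table 1 rules only inform the decision, all available safety data are reviewed (Section 3.2.1), and the team adjudicates high-grade events as potentially dose-limiting (Section 9.5). On the Grade 3 reading, Section 3.2.1 is itself a written hold. What remains is that step 1 says otherwise.

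**Conclusion.** The two conditions differ, and a single non-DLT Grade 3 event exposes the difference. This rests on reading severe as Grade 3 or higher, which is the better-supported reading but not the only one. The ordering within step 1, two Grade 2 events above one Grade 3 event, does not depend on that reading.

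The size cannot be stated, because the documents do not give the frequency of such an event in the first subject. A reader might take the 4% to 44% at n = 3, or the 0.3% to 27.9% at n = 6, as the cost of the gap. They are not: they compare one with three subjects whatever the first subject experienced, and so price the sponsor's stated choice to limit subtherapeutic exposure.

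The risk is bounded by evaluability without a DLT, by team review and adjudication, by the need for at least three evaluable subjects at DL2 with only one dosed on the first day and others at least 48 hours later, and by the 34-fold margin. The documents do not say whether DL1 is complete; if it is, the change matters mainly for consistency and for any return to DL1. Severity: minor.

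**What to change.** Use one trigger everywhere. In Section 10.2.1 step 1, treat two additional subjects at DL1 if the first subject has any of:

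- a DLT;
- any non-hematologic toxicity of Grade 3 or higher, other than Grade 3 fatigue as exempted in Table 6;
- two or more toxicities of Grade 2 or higher.

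Events clearly due to the underlying disease or an extraneous cause do not count, as in Section 5.9.1. Otherwise escalate.

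Have Section 3.2.1 and the synopsis refer to this trigger, but keep their severe-toxicity condition for hematologic events not clearly due to the underlying disease. It should not simply be dropped: the hematologic row of Table 6 covers only neutrophils and platelets and does not apply to patients with active leukemia. The attribution limit is needed because Section 9.1.4 describes myelosuppression as common in these subjects. Naming the fatigue exemption makes it a visible choice, and writing Grade 2 or higher settles the present ambiguity.

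The cost is an amendment to three places and, when triggered, up to two more subjects at a potentially subtherapeutic dose with their 56-day DLT period. If g is the probability that the new wording triggers where the current one does not, expected DL1 enrolment rises by 2g. For assumed values of g of 0.05, 0.10 and 0.20, that is 0.1, 0.2 and 0.4 subjects.

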## Study Phase and Cohorts

A BOPIN design will be utilized to determine the MTD of NC525, where a minimum of 3 evaluable subjects will be enrolled in each dose level from Cohort 2 onwards. In the case of the starting dose level (2mg/kg), a minimum of 1 evaluable subject may be enrolled (in the absence of severe toxicity) prior to determining escalation to the next dose level given the dose is an approximation of the minimally active dose (PD30).

[figure not shown]
All dose escalation and de-escalation decisions will be based on the occurrence of DLTs at a given dose during the first 56-day period (i.e., first 2 cycles), also referred to as the DLT observation period ([Figure S3](#)), and will be made jointly by the Clinical Study Team comprised of the Sponsor (Chief Medical Officer and Medical Monitor), CRO Medical Monitor and Investigators once the minimum number of evaluable subjects (n=3) have completed the DLT observation period.

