**Table 14: Operating characteristics of the BOIN design**

	Dose Level					Number of Patients	% Early Stopping
	1	2	3	4	5		
Scenario 1							
True DLT Rate	0.25	0.41	0.45	0.49	0.53		
Selection %	67.6	16.9	6	1.4	0.2		7.9
% Pts Treated	43.5	34.3	17.6	3.9	0.7	18.4	
Scenario 2							
True DLT Rate	0.12	0.25	0.42	0.49	0.55		
Selection %	25.9	53.5	16.9	2.8	0.2		0.7
% Pts Treated	24.2	41.1	27.1	6.4	1.1	21.2	
Scenario 3							
True DLT Rate	0.04	0.12	0.25	0.43	0.63		
Selection %	1.8	23.8	60.5	13.5	0.4		0
% Pts Treated	8.4	25.7	41.8	20.6	3.4	22.1	
Scenario 4							
True DLT Rate	0.02	0.06	0.1	0.25	0.4		
Selection %	0.3	2.3	21.4	58.3	17.7		0
% Pts Treated	5.3	8.6	30.3	37.3	18.5	22.9	
Scenario 5							
True DLT Rate	0.02	0.05	0.08	0.11	0.25		
Selection %	0.5	0.9	7.3	22.1	69.2		0
% Pts Treated	5.2	7.5	20.6	30.4	36.4	21.6	

**Note:** "% Early Stopping"" refers to early stopping due to excessive DLT.

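### Table 14 simulates a different escalation design: it has five dose levels where six are planned, and its level 2 averages of 2.0 and 1.6 subjects cannot arise under the written titration rule (floor 2.8).

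*Combined protocol and SAP*

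**What the plan says.** **Dose levels.** Section 3.2.2 and Table 2, and the matching synopsis text and Table S2, plan six levels: 2, 2.5, 4.5, 10, 20 and 30 mg/kg. Section 1.2.1 still lists five, without 2.5 mg/kg.

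**Titration.** Section 10.2.1 treats one subject at DL1. It adds two more after a DLT or two or more grade 2 toxicities; "otherwise escalate to DL2 and hereafter treat subjects in cohort size of 3". Section 3.2.1 says "a minimum of 3 evaluable subjects will be enrolled at each level from Cohort 2 onwards", and the synopsis says the same ("a minimum of 3 evaluable subjects will be enrolled in each dose level from Cohort 2 onwards"). Section 3.2.1 also names the first dose as the only exception to treating three before escalating.

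**Stopping.** Escalation ends at 30 subjects, or when 9 evaluable subjects are at the current dose and "the decision according to the rules described in Step 2 is to stay at the current dose". Section 10.2.1 also says "the maximum sample size per cohort is 12".

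**Simulation.** The escalation sample size is described as "chosen to be consistent with typical phase I oncology trials and calibrated using simulation". The only escalation simulation shown is "Table 14: Operating characteristics of the BOIN design", from 1000 simulated trials on five dose levels. The text introduces it as "showing that the design selects the true MTD, if any, with high probability and allocates more patients to the dose levels" nearest the target.

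**The concern.** A table of operating characteristics supports a design only if that design was the one simulated. Table 14 differs from the written plan in two ways: the number of levels, and apparently where single-subject titration applies. If so, the selection percentages, the subjects per level and the mean sample size are another design's results, and the statement that the sample size was calibrated by simulation has no demonstration behind it for the plan as it stands.

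**Working it through.** **1. Subjects at level 2, from Table 14 (share treated × mean N)**

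- Scenario 4: 0.086 × 22.9 = 1.97 (1.95–1.99 allowing for rounding).
- Scenario 5: 0.075 × 21.6 = 1.62 (1.61–1.63).

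**2. Lowest mean the written rule allows**

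The DLT rate at level 1 is 0.02 in both scenarios. Every trial that reaches DL2 treats at least 3 subjects there.

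- First subject at DL1 has no DLT and the grade 2 trigger does not fire: 3 × 0.98 = 2.94.
- Grade 2 trigger always fires, counting only trials with 0 of 3 DLTs at DL1: 3 × 0.98³ = 2.82.

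The shortfalls against the lower floor are 2.82 − 1.97 = 0.85 and 2.82 − 1.62 = 1.20. With a per-trial SD of about 2.0–2.5, the standard error over 1000 trials is about 0.06–0.08, so both are more than ten standard errors. This bound needs no simulation and does not depend on how the stop at 9 or the limit of 12 is read.

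**3. Could the columns be DL2 to DL6?**

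Column 1 would then average 0.053 × 22.9 = 1.21 and 0.052 × 21.6 = 1.12 subjects in scenarios 4 and 5, again below the minimum of 3 from Cohort 2 onwards.

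**4. What does reproduce the table?**

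The section 10.2.1 algorithm was simulated with Table 1 boundaries, a maximum of 30 and isotonic MTD selection, 20,000 trials per cell. The stop at 9 was read two ways. *Literal* means Table 1 says stay. *Wide* also counts cases where step 2 keeps the next subjects at the same dose, such as an escalate decision at the top level. Each was run with and without the limit of 12, taken as stopping when the next assigned dose already holds 12.

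Root mean square error against Table 14, in subjects per level over 25 cells:

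| Five levels, single subjects at | Wide, no limit | Wide, limit | Literal, limit | Literal, no limit |
|---|---|---|---|---|
| DL1 and DL2 | 0.09 | 0.23 | 0.27 | 0.87 |
| DL1 only | 0.87–1.28 over the four readings | | | |

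The best fit (DL1 and DL2, wide, no limit) against the table:

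| Quantity | Simulated | Table 14 |
|---|---|---|
| Mean N, scenarios 1–5 | 18.1/21.2/22.1/23.2/21.9 | 18.4/21.2/22.1/22.9/21.6 |
| Correct selection %, scenarios 1–5 | 68.5/55.0/60.0/57.0/67.3 | 67.6/53.5/60.5/58.3/69.2 |
| Level 2 mean, scenarios 4, 5 | 2.02, 1.66 | 1.97, 1.62 |

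With DL1-only titration on five levels, the level 2 means are 4.1–4.2 and 3.8–3.9 under every reading. In scenario 1, Table 14 puts 0.176 × 18.4 = 3.24 subjects at level 3. DL1-only gives 1.6; DL1 and DL2 gives 2.9–3.0.

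**5. The plan as written: six levels, DL1 only**

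The documents give no DLT rate for the added level. It was placed at 1%, 50% and 99% of the gap between Table 14's level 1 and level 2 rates. Ranges cover those placements, both stop readings, and runs with and without the limit of 12. A separate 12,000-trial run is included; it set the low end of scenario 3 selection.

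| Scenario | Correct selection % | Table 14 | Mean N | Table 14 |
|---|---|---|---|---|
| 3 | about 47–55 | 60.5 | about 24–26 | 22.1 |
| 4 | about 51–54 | 58.3 | about 26–27 | 22.9 |
| 5 | about 63–66 | 69.2 | about 25.5–27 | 21.6 |

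Against a five-level, DL1-and-DL2 run under the same reading, selection falls by about 5–12 points in scenario 3 and 3–6 in scenario 4. There is no clear change in scenario 5 (between 1 point higher and 3 lower, where Table 14's own standard error is about 1.5). Mean N rises by about 1.5 to 4. If the grade 2 trigger fired in every DL1 subject, selection would be at least 45/50/62% and mean N at most 26.7/28.0/28.2. Scenarios 1 and 2 depend too heavily on the assumed rate to be informative on six levels. The Table 2 increments and backfill were not modelled.

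**The case against.** The strongest reply is that little turns on this. On Table 14's own five levels, where no rate has to be assumed, DL1-only titration gives selection of about 70/58–59/57/56/65% and mean N of about 16.7/20.6/22.7/24.4/23.3. Like for like, that is a selection change of about 3 points or so and a mean N change of less than 2 subjects, with the written rule selecting better in scenarios 1 and 2. In scenario 1, Table 14 overstates exposure at level 3, whose true DLT rate is 0.45. The larger differences in step 5 therefore come mostly from adding a sixth level to scenarios built for five. The low end of the scenario 3 range needs the added level to be almost as toxic as the old level 2. Table 1 depends only on counts at the current dose, so no decision boundary changes, and the dose levels are in any case only planned.

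All of that stands, and it limits the consequence. It is also fair that the origin of the table is inferred: the documents do not mention titration at DL2, and the literal stop reading without the limit of 12 fits no better (0.87) than the best DL1-only run (0.87). None of this answers the two mismatches. The level count can be read off the page, and the floor of 2.8 holds whatever produced the table.

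**Conclusion.** The concern holds. Table 14 is not the operating characteristics of the written escalation design. The level count and the level 2 floor establish this without assumptions. That the table came from a five-level design with single subjects at DL1 and DL2 is a well-supported inference only.

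The size is approximate and rests on the assumed rate for the added level: printed selection is higher than recomputed by roughly 6–13 points in scenario 3 (60.5 against 47–55), 4–7 in scenario 4 (58.3 against 51–54) and 3–6 in scenario 5 (69.2 against 63–66), and mean N is understated by about 2 to 5 subjects. The like-for-like changes are smaller, and not clear for selection in scenario 5. Every recomputed mean N is below the ceiling of 30, no boundary is shown to be unsafe, and the dose with a true rate of 0.25 still receives the most subjects in scenarios 3–5. This should be fixed, but it does not show that the design fails.

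**What to change.** Either re-run Table 14 for the plan as written, or reconcile sections 1.2.1, 3.2.1, 3.2.2, Table 2 and 10.2.1 (and the synopsis) with the design that was simulated.

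A re-run should use six levels, a single subject at DL1 only, the Table 1 boundaries and the maximum of 30. It should state:

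- the DLT rates assumed for all six levels;
- which reading of the stop at 9 applies;
- what the limit of 12 does;
- whether the grade 2 trigger and the Table 2 increments are modelled.

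Then restate the selection percentages, subjects per level and mean N, and word the sentence introducing the table to match the new results.

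The cost is simulation time and restated text, and some figures may look less favourable. No patients are added and the limit of 30 is unchanged.
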